8.5.1.3. Criteria for Calculating AUC

The minimum requirement for the calculation of AUC will be the inclusion of at least 3 consecutive concentrations above the lower limit of quantification. If there are only 3 consecutive concentrations, at least 1 should follow C_{max} .

If the extrapolated area is 30%, $AUC_{0-\infty}$ (and derived parameters CL/F, V_z/F , $t_{1/2}$ etc) may be excluded from summary statistics and statistical analysis at the discretion of the sponsor or PK analyst.

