**Study design:**

This will be a single SC dose study.

Doses will be administered in an escalating manner following satisfactory review by a Protocol Safety Review Team (PSRT) of the safety, tolerability and PK data through Day 6 from the lower dose levels.

This study will comprise a placebo-controlled, double-blind, single-dose, sequential-group design in healthy subjects. Each subject will participate in 1 treatment period and reside in the Clinical Research Unit (CRU) from Day -1 through Day 6. It is planned for 6 subjects per dose level group to receive SC CPT31 and 2 subjects to receive matching placebo. Each group will be divided into 2 cohorts, with each cohort being dosed 72 hours apart. Sentinel dosing will take place in the first cohort, which will comprise 2 subjects, with 1 subject receiving CPT31 and 1 subject receiving placebo. The second cohort will comprise 6 subjects, with 5 subjects receiving CPT31 and 1 subject receiving placebo.

Blood samples for PK analysis and assessment of immunogenicity will be collected predose and up to 5 days postdose, with an additional immunogenicity sample taken at the Follow-up visit.

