### 1.5. Summary of Nonclinical Pharmacokinetics

Following intravenous (IV) or SC administration (1 mg/kg) in Sprague-Dawley rats, the apparent plasma terminal elimination half-life (t1/2) of CPT31 was 3.2 and 5.5 hours, respectively, and SC bioavailability was 53%. Similarly, following IV or SC administration (1 or 3 mg/kg, respectively) in cynomolgus macaques, the t1/2 of CPT31 was 7 and 18.6 hours, respectively, and SC bioavailability was 78%. CPT31 given IV to Sprague-Dawley rats or monkeys has a low volume of distribution (134 mL/kg and 96 mL/kg, respectively), suggesting that it is largely confined to the plasma compartment. Plasma protein binding studies revealed that 5  $\mu$ M CPT31 is  $\geq$ 96% bound in rat, minipig, dog, monkey, and human plasma.

Both Cmax and AUC of CPT31 upon SC administration to Sprague-Dawley rats are linear (but not fully dose proportional) at increasing dose levels up to 40 mg/kg. Terminal half-life is consistently between 4 and 8 hours at dose levels ranging from 3-75 mg/kg.

A distribution/excretion study using radioactive [I]-CPT31 suggested that CPT31 is eliminated via renal clearance, as expected for a mid-molecular weight compound (average 9,029 Daltons). Composed of D-peptides, CPT31 is not expected to enter peptide catabolic pathways.

Non-parametric superposition of available cynomolgus macaques PK data (Table 1) and allometric scaling to humans predicts that a 0.03 mg/kg SC injection every third day would give a trough level  $\sim$ 13-22 nM (117-199 ng/mL). Therefore, this dose is tentatively set as the expected human therapeutic dose in order to achieve a trough CPT31 level of  $\geq$ 4  $\times$  the

serum-adjusted IC90 against diverse strains in human PBMCs (~16 nM), as described above. However, the PK profile in humans remains to be established, and the estimated effective dosing will change accordingly.

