### 3.5. Selection of Doses in the Study

Based on activity in human PBMCs infected with diverse primary isolates, the estimated effective serum trough concentration of CPT31 is 16 nM (145 ng/mL) (4x the serum-adjusted IC90 in PBMCs).

Human PK modeling predicts that a dose of 0.03 mg/kg administered every third day will be optimal to maintain CPT31 serum trough levels in a narrow range (~13-22 nM, 117-199 ng/mL) that is close to the target trough concentration of 16 nM while minimizing total exposure (Cmax ~50 nM, 452 ng/mL) over the course of an envisioned future short-duration (~2-week) multiple ascending dose human study. We propose a starting dose of 0.01 mg/kg in this first-in-human single ascending dose study, with subsequent dose escalations to 0.04 mg/kg (4-fold increase), 0.12 mg/kg (3-fold increase), and 0.24 mg/kg (2-fold increase). The safety margins for the 0.01 mg/kg human dose relative to rat and monkey NOAELs are 97 and 320, respectively (Table 2).

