8.5.1.2. Criteria for Calculating an Apparent Terminal Elimination Half-life

The start of the terminal elimination phase for each subject will be defined by visual inspection and will be the first point at which there is no systematic deviation from the log-linear decline in plasma concentrations.

The apparent terminal elimination rate constant (λ_z) will only be calculated when a reliable estimate can be obtained using at least 3 data points, preferably not including C_{max} , and the adjusted coefficient for determination of exponential fit (R^2 -adj) of the regression line is ≥ 0.7 . Parameters requiring λ_z in their calculation (eg, AUC_{0-inf} , $t_{1/2}$, CL/F and V_z/F) will only be calculated if the R^2 -adj value of the regression line is ≥ 0.7 .

The following regression-related diagnostic PK parameters will be determined:

Parameter	Units	Definition
λ_z	h^{-1}	apparent terminal elimination rate constant
λ_z Upper	h	end of exponential fit
λ_z Lower	h	start of exponential fit
λ_z N	NA	number of data points included in the log-linear regression
λ_z Span Ratio	NA	time period over which λ_z was determined as a ratio of $t_{1/2}$
R^2 -adj	NA	adjusted coefficient for determination of exponential fit

The time period used for the estimation of apparent terminal elimination half-lives, where possible, will be over at least two half-lives. For $t_{1/2}$ estimates where λ_z was calculated over a time period less than twice their resultant half-life, the reliability of $t_{1/2}$ and any PK parameters derived from λ_z will be discussed in CSR.

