8.5.1.4. Treatment of Outliers in Pharmacokinetic Analysis

If a value is considered to be anomalous due to being inconsistent with the expected PK profile, it may be appropriate to exclude this point from the PK analysis. However, the exclusion of data must have strong justification and will be documented in CSR.

Quantifiable predose concentration values in the first dosing will be considered anomalous and set to missing for the PK analysis.

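### SAP 8.5.1.3 leaves high-extrapolation AUC0-∞, CL/F, Vz/F and t1/2 to be kept or dropped case by case, which can selectively remove long half-lives

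*SAP*

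**What the plan says.** SAP 8.5.1.3 sets its trigger with the words "If the extrapolated area is 30"%. No inequality sign is visible; I read it as above 30% and make nothing of the gap. Once triggered, AUC0-∞ and the parameters the section calls derived from it (CL/F, Vz/F, t1/2) "may be excluded from summary statistics and statistical analysis at the discretion of the sponsor or PK analyst".

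Other provisions bear on the same values:

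- SAP 8.5.1.2 obtains t1/2 from λz. It requires at least 3 points and an adjusted R² of at least 0.7. Where λz was "calculated over a time period less than twice their resultant half-life", it asks for the reliability of t1/2 and other λz-based parameters to be discussed in the CSR.
- SAP 8.5.1.4, on anomalous values, says that "the exclusion of data must have strong justification and will be documented in CSR".
- SAP 8.5.1 reports %AUCextrap and allows, but does not require, an AUC to a fixed time when AUC0-∞ is not available for everyone. No time point is named.
- SAP 8.5.3 lists all PK parameters and examines dose proportionality for Cmax, AUC0-tlast and AUC0-∞.

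**The concern.** The choice is made after the values are known, subject by subject, and nothing requires it to be the same across subjects or doses. SAP 8.5.1.4 demands justification and documentation to drop a single anomalous value; 8.5.1.3 demands neither to drop a subject's main exposure parameters. Because the SAP permits the exclusion, using it is not a deviation that the SAP Introduction would require the CSR to identify.

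Including t1/2 is the weakest part. It does not depend on AUC0-∞, and where the 120 h window sets the extrapolated share, a high share and a long half-life largely coincide. Dropping t1/2 on that ground selects on the quantity being summarised.

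At stake are the geometric means of t1/2, AUC0-∞ and CL/F, from six active subjects per dose, in data that Protocol 1.6 says will help establish doses and regimen for later studies.

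**Working it through.** The documents give no figure for this point, so there is none to reproduce.

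**Inputs from the documents**
- Sampling: "Blood samples for PK analysis and assessment of immunogenicity will be collected predose and up to 5 days postdose" (Protocol synopsis); the last scheduled PK sample is at 120 h (Protocol Appendix 6).
- Projected human profile at 0.03 mg/kg every third day (Protocol 3.5): Cmax about 50 nM (452 ng/mL), trough "in a narrow range (~13-22 nM, 117-199 ng/mL").
- Monkey SC half-life 18.6 h (Protocol 1.5).
- Six active subjects at each of four doses (Protocol 3.1).

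**Assumed:** between-subject CV of half-life 30% (range 20–40%). No human half-life or CV is stated.

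**Step 1: half-life at the 30% limit.** For a mono-exponential decline with no truncation at the LLOQ, the extrapolated share is 2^(−120/t1/2). Setting it to 0.30 gives t1/2 = 120 × ln 2 / ln(1/0.30) = 69.1 h. If the decline starts 16 h postdose, the window is 104 h and the limit is 59.9 h.

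**Step 2: half-life implied by Protocol 3.5.** t1/2 = (72 − Tmax) × ln 2 / ln(Cmax/trough).
- Tmax 0: 72 × ln 2 / ln(452/117) = 36.9 h; 72 × ln 2 / ln(452/199) = 60.8 h.
- Tmax 12 h: 30.8 h and 50.7 h.

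The extrapolated share is 10.6% at 37 h and 25.6% at 61 h, so slower subjects would cross 30%. At 18.6 h it is 1.1%.

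**Step 3: effect of dropping every subject above the limit.** Take half-life as lognormal with median m, σ = √ln(1 + CV²) = 0.294 at CV 30%, and z = ln(69.1/m)/σ. The share dropped is 1 − Φ(z). The geometric mean changes by exp(−σφ(z)/Φ(z)) − 1.

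| Median t1/2 (h) | z | Share dropped | Change in geometric mean t1/2 |
|---|---|---|---|
| 18.6 | 4.47 | about 0% | about 0% |
| 37 | 2.13 | 1.7% | −1.2% |
| 50 | 1.10 | 13.5% | −7.1% |
| 61 | 0.42 | 33.6% | −14.9% |

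At 61 h the change is −8.4% for CV 20% and −20.8% for CV 40%. A share of 33.6% is about 2 of 6 subjects per dose.

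**Step 4: simulated noncompartmental analysis.** 500 trials per scenario used the protocol's sampling times, four doses with six active subjects and a true slope of 1. Everyone above 30% was dropped. Assumed: one-compartment SC model, volume 96 mL/kg (the monkey IV value), absorption half-life 4 h, CV 30% for clearance, 20% for volume and about 30% for absorption rate, 10% assay error. The adjusted R² filter was not applied.

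With a negligible LLOQ:

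| Median t1/2 (h) | Dropped | t1/2 | Dose-normalised AUC0-∞ |
|---|---|---|---|
| 18.6 | about 0% | 0% | 0% |
| 37 | 7% | −6% | −4% |
| 49 | 24% | −15% | −10% |
| 61 | 44% | −25% | −17% |

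CL/F is dose over AUC0-∞, so its geometric mean (per kg) would rise by about 4%, 11% and 20% in the last three rows (1/0.96, 1/0.90, 1/0.83). In at least 99% of dose groups with any exclusion, the longest half-life was among those dropped.

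These effects exceed Step 3 partly because half-life varies more here. If clearance and volume vary independently, the combined CV is √(1.09 × 1.04 − 1), about 37%. Absorption also shortens the usable window, and λz carries estimation error.

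**Step 5: when the LLOQ ends the profile.** The documents leave the LLOQ to separate assay documents. At an assumed 20 ng/mL and t1/2 of 18.6 h, 42% of the lowest-dose subjects were dropped against under 1% at each other dose, and the longest half-life was among those dropped in only 78% of affected groups. At 49 h the figures were 36% at the lowest dose against 23–24%.

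**Step 6: AUC0-∞ power-model slope (true value 1), all estimable subjects against those kept.**
- Negligible LLOQ: 0.995–1.003 against 0.996–1.004.
- LLOQ 20 ng/mL: 0.958–1.002 against 0.967–0.991.
- LLOQ 40 ng/mL: 0.886 against 0.970 (t1/2 18.6 h); 0.941 against 0.992 (49 h).

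**The case against.** Four stronger readings are tempting, and the documents do not support them.

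- *The summaries will be biased.* The clause is permissive, and the figures above assume it is used on everyone over the limit. Near the monkey half-life with a low LLOQ there is almost nothing to exclude.
- *Dose proportionality is biased.* Step 6 does not show it. Uniform exclusion left the slope almost unchanged, and at the highest assumed LLOQ it moved the slope towards 1. Cmax and AUC0-tlast are also tested and are untouched by the clause. What stands is that selective or dose-uneven use is allowed; its effect is not quantified.
- *High extrapolation simply means a long half-life.* That fails where the LLOQ ends the profile, as Step 5 shows.
- *SAP 8.5.1.2 and 8.5.1.3 contradict each other.* Section 8.5.1.2 asks for discussion in the CSR; it does not say the values stay in the summaries. Both can apply.

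There is also a sound reason for caution with these values. A half-life of 69 h needs 138 h to span two half-lives, more than the 120 h sampled, so without truncation these subjects already fall under the reliability clause of 8.5.1.2. That supports flagging and discussion, not unrecorded removal.

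The practical damage is also limited. All parameters are listed and %AUCextrap is reported, so a reader could rebuild the full summaries. PK is a secondary objective, and SAP 8.1 urges caution because the sample size is not based on power. These points lower the weight of the concern but do not justify an open discretion.

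**Conclusion.** The concern holds in limited form. SAP 8.5.1.3 permits outcome-dependent, undocumented exclusion in groups of six and wrongly classes t1/2 as derived from AUC0-∞. Where the 120 h window governs, exclusion can lower summarised t1/2 and AUC0-∞ and raise CL/F.

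If all subjects above 30% were dropped, geometric mean t1/2 would change by about −1% to −15% for medians of 37 to 61 h at an assumed CV of 30%, by up to about −25% in the simulation, and by about 0% at 18.6 h. The 37–61 h range is inferred from the projected peak and troughs in Protocol 3.5, counting the full 72 h from the peak; it is not a stated human half-life. The CL/F figures rest on the simulation's assumptions. The direction for Vz/F was not examined. For proportionality, the remaining risk is uneven use of the discretion.

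**What to change.** 1. Decide whether t1/2 is included only by the criteria in SAP 8.5.1.2, not by %AUCextrap.
2. Replace the discretion in SAP 8.5.1.3 with one rule: flag AUC0-∞, CL/F and Vz/F above the stated limit for every subject alike. Show the summaries and the AUC0-∞ power model with and without the flagged values, and report the number flagged per dose in the CSR.

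Naming a fixed-time AUC in advance would help but is optional, since SAP 8.5.1 already allows one.

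The cost is a SAP wording change, one repeated table and one repeated model. The downside is that one version of the results includes less precise AUC0-∞ values, which are flagged. No new data are needed.

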8.5.1.4. Treatment of Outliers in Pharmacokinetic Analysis

If a value is considered to be anomalous due to being inconsistent with the expected PK profile, it may be appropriate to exclude this point from the PK analysis. However, the exclusion of data must have strong justification and will be documented in CSR.

Quantifiable predose concentration values in the first dosing will be considered anomalous and set to missing for the PK analysis.

8.5.2. Presentation of Pharmacokinetic Data

8.5.2.1. Presentation of Plasma Drug Concentration Data

If the actual time of sample collection deviates from the nominal time by more than $\pm 10\%$, the concentration will be flagged and excluded from the summary statistics. Individual concentrations deemed to be anomalous will be flagged in the listings and excluded from the summary statistics.

For PK concentration data the following rules will apply:

- Values that are BLQ will be set to 0 for the calculation of summary statistics.
- Arithmetic mean or median values that are BLQ will be presented as 0.
- If any BLQ results (treated as 0) are in a series of summarized data, geometric mean and coefficient of variation (CV%) of geometric mean will be reported as not calculated (NC).

8.5.2.2. Presentation of Plasma Pharmacokinetic Parameter Data

The PK parameters will be listed and summarized descriptively by treatment (arithmetic and geometric means; standard deviation and CV%; minimum, maximum, and median values; and geometric CV). For T_{max} and T_{last} , no geometric mean and geometric CV will be calculated.

For the calculation of summary statistics of PK parameters, all not reported (NR) and NC values in a data series will be set to missing.

8.5.3. Pharmacokinetic Statistical Methodology

All PK concentrations and parameters will be listed.

Summary tables, mean (\pm standard deviation [SD]) figures, overlaying individual figures, and individual figures by treatment and time postdose will be provided for plasma PK concentrations. All figures will be produced on both linear and semi-logarithmic scales, with the exception of figures across all days, which will be produced on the linear scale only. The \pm SD bars will only be displayed on the linear scale.

Summary tables by treatment will be provided for all PK parameters, with the exception of diagnostic regression-related PK parameters. Separate summary tables by treatment and time interval will be provided for excretion parameters and cumulative excretion parameters.

Where data are available, CPT31 dose proportionality will be examined across dose groups. The PK parameters (C_{max} , $AUC_{0-tlast}$, $AUC_{0-\infty}$) will be analysed for dose proportionality using a power model approach or analysis of variance (ANOVA) model, as appropriate. The PK parameters will be analyzed using a power model³ that will have the following form:

$$\text{parameter} = \text{intercept} \times \text{dose}^{\text{slope}} + \text{random error}$$

Using the natural log (ln) transformation,⁴ a power model can be expressed as a linear regression equation:

$$\ln(\text{parameter}) = \text{intercept} + \text{slope} \times \ln(\text{dose}) + \text{random error}$$

For dose proportionality, the slope of the regression line is equal to 1; for dose independence, it is equal to 0.

For each PK parameter separately, a pooled estimate (across all doses) of slope, corresponding 95% confidence interval (CI), and between-subject CV will be calculated. Figures (on the logarithmic scale) containing individual values, power model line (95% CI), and dose proportionality line (defined as the power model line with slope of 1) will be created for each PK parameter; figures (on the semi-logarithmic scale) containing individual values and geometric means will be created for each corresponding PK parameter normalized by dose administered.

8.6. Safety and Tolerability Assessments

8.6.1. Adverse Events

All AEs will be coded using the Medical Dictionary for Regulatory Activities (MedDRA) Version 23.0 (or higher if upversioned during the study). All AEs will be assigned severity grade using the following criteria defined by the Division of AIDS Table for Grading the Severity of Adult and Pediatric Adverse Events, Version 2.1 dated July 2017:

- **Grade 1, Mild:** Usually transient and may require only minimal treatment or therapeutic intervention. The event does not generally interfere with usual activities of daily living.

- **Grade 2, Moderate:** Usually alleviated with additional specific therapeutic intervention. The event interferes with usual activities of daily living, causing discomfort but poses no significant or permanent risk of harm to the subject.
- **Grade 3, Severe:** Interrupts usual activities of daily living, or significantly affects clinical status, or may require intensive therapeutic intervention.
- **Grade 4, Potentially Life-threatening:** The subject was at immediate risk of death from the event as it occurred (i.e., does not include a reaction that might have caused death if it had occurred in a more serious form). For instance, drug-induced hepatitis that resolved without evidence of hepatic failure would not be considered life-threatening even though drug-induced hepatitis can be fatal.
- **Grade 5, Death.**

A treatment-emergent adverse event (TEAE) will be defined as an AE that starts during or after dosing, or starts prior to dosing and increases in severity after dosing.

A treatment-related TEAE will be defined as a TEAE with a relationship of possibly, probably, or definitely related to the study treatment, as determined by the investigator.

All AEs will be listed. In addition to the data recorded in the database, the listings will include derived onset time and duration. Onset time will be calculated from the time of dosing for TEAEs only.

The frequency of subjects with TEAEs and the number of TEAEs will be summarized for the following categories:

- TEAEs (overall, serious, leading to discontinuation, and leading to death) by treatment
- TEAEs by severity and treatment
- Treatment-related TEAEs (overall, serious, leading to discontinuation, and leading to death) by treatment
- Treatment-related TEAEs by severity and treatment

The frequency of subjects will be summarized separately for TEAEs and treatment-related TEAEs by the following:

- System organ class, preferred term, and treatment
- Preferred term and treatment

For the AE data the following rules will apply:

- For the derivation of TEAE status: If the start date/time of an AE is incomplete or missing, an AE will be assumed to be a TEAE, unless the incomplete start date/time or the end date/time indicates an AE started prior to dosing.

- For the derivation of treatment-related TEAE status: If the study treatment relationship for a TEAE is missing, a TEAE will be assumed to be a treatment-related TEAE.
- For the derivation of onset time: If the start date/time of an AE is missing, onset time will not be calculated. If the start date/time of an AE is incomplete, where possible, the minimum possible onset time will be calculated and presented in ‘ \geq DD:HH:MM’ format (eg, if the date/time of dosing is 01MAY2019/08:00 and recorded start date/time of an AE is 03MAY2019, then the minimum possible onset time will be calculated by assuming the AE started at the first hour and minute of 03MAY2019 [03MAY2019/00:00], thus will be presented as onset time \geq 01:16:00 in the listing).
- For the derivation of duration: If the end date/time of an AE is missing, duration will not be calculated. If the start or end date/time of an AE is incomplete, where possible, the maximum possible duration will be calculated and presented in ‘ \leq DD:HH:MM’ format (eg, if the start of an AE date/time is 01MAY2019/08:00 and its recorded end date/time is 03MAY2019, then the maximum possible duration will be calculated by assuming the AE ended at the last hour and minute of 03MAY2019 [03MAY2019/23:59], thus will be presented as duration \leq 02:15:59 in the listing).
- For the calculation of summary statistics: If the severity of a TEAE is missing, a TEAE will be counted under the maximum severity possible.
- For the calculation of summary statistics: If a subject experienced multiple TEAEs with the same preferred term for the same treatment, this will be counted as 1 TEAE for that treatment under the maximum severity recorded.

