### Relationship to Study Treatment

The Investigator (or designee) will make a determination of the relationship of the AE to the study drug using a 4-category system according to the following guidelines:

- **Not Related:** The AE is definitely caused by the subject's clinical state or the study procedure/conditions.
- **Unlikely Related:** The temporal association between the AE and the drug is such that the drug is not likely to have any reasonable association with the AE.
- **Possibly Related:** The AE follows a reasonable temporal sequence from the time of drug administration but could have been produced by the subject's clinical state or the study procedures/conditions.

- **Related:** The AE follows a reasonable temporal sequence from administration of the drug, abates upon discontinuation of the drug, follows a known or hypothesized cause-effect relationship, and (if appropriate) reappears when the drug is reintroduced.

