### **Follow-up of Adverse Events**

Every reasonable effort will be made to follow up with subjects who have AEs. Any subject who has an ongoing AE that is possibly related or related to the IMP or study procedures at the Follow-up visit will be followed up, where possible, until resolution or until the unresolved AE is judged by the Investigator (or designee) to have stabilized. This will be completed at the Investigator's (or designee's) discretion. Any subject who has an ongoing AE that is not related or unlikely related to the IMP or study procedures at the Follow-up visit can be closed out as ongoing at the Investigator's discretion.

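### The SAP's causality terms for a treatment-related TEAE do not match the protocol's four-category scale, and the protocol's strongest category, 'Related', is neither named nor mapped

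*SAP*

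**What the plan says.** Under Relationship to Study Treatment in protocol Appendix 1, the investigator, or someone acting for the investigator, "will make a determination of the relationship of the AE to the study drug using a 4-category system according to the following guidelines". The four categories are Not Related, Unlikely Related, Possibly Related and Related. 'Possibly Related' begins "The AE follows a reasonable temporal sequence from the time of drug administration but could have been produced by" and goes on to name alternative explanations: clinical state, or the procedures and conditions of the study. 'Related', the top of the scale, begins "The AE follows a reasonable temporal sequence from administration of the drug, abates upon discontinuation of the drug" and adds further conditions. In the same appendix, Follow-up of Adverse Events treats the two upper categories as one set: "Any subject who has an ongoing AE that is possibly related or related to the IMP or study procedures".

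SAP section 8.6.1 uses other terms: "A treatment-related TEAE will be defined as a TEAE with a relationship of possibly, probably, or definitely related to the study treatment", as judged by the investigator. It adds a rule for gaps: "If the study treatment relationship for a TEAE is missing, a TEAE will be assumed to be a treatment-related TEAE". It also says: "All AEs will be listed. In addition to the data recorded in the database, the listings will include derived onset time and duration".

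The SAP maps neither scale to the other. Section 1 says that it was written after review of protocol version 4.0 and the eCRF, and that it takes precedence over the protocol's statistical considerations. Section 10 declares no significant change from the protocol's analyses.

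**The concern.** The flag for a treatment-related TEAE is built from the recorded causality category. If the database holds the protocol's four categories, two of the SAP's three qualifying terms can never occur, and the category carrying the strongest attribution is not on the qualifying list. A programmer who codes the sentence as it stands would set the flag for 'Possibly Related' and for missing causality, but not for 'Related'.

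The flag drives a whole family of outputs: treatment-related TEAEs overall, serious, leading to discontinuation and leading to death; by severity; by system organ class and preferred term; and by preferred term alone. AE incidence and severity is the first-listed primary endpoint, and this is a first-in-human study, so readers will look closely at these tables. Any error from literal coding would run in one direction, towards too few treatment-related events.

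**Working it through.** No figure in the plan is in dispute. The check is a comparison of labels, followed by one small calculation.

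**Step 1: compare the scales.** The inputs are the four categories in protocol Appendix 1 and the three qualifying terms and missing-value rule in SAP 8.6.1.

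| Recorded relationship | Matching SAP 8.6.1 term | Treatment-related under literal matching? |
|---|---|---|
| Not Related | none | No |
| Unlikely Related | none | No |
| Possibly Related | possibly | Yes |
| Related | none | No |
| Missing | separate rule | Yes |

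The SAP terms 'probably' and 'definitely' match no protocol category. Of the two protocol categories that express a causal link, the literal rule captures 1 of 2.

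**Step 2: look for a mapping elsewhere.** The SAP gives none, and section 10 does not present the different terms as a change. The protocol's follow-up rule joins 'possibly related' and 'related', which shows the set that the protocol has in mind.

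**Step 3: trace the outputs.**
- Dependent on the flag: all the treatment-related TEAE summaries in SAP 8.6.1.
- Not dependent on it: the all-cause TEAE tables, the AE listings, and the stopping rules in protocol sections 3.7 and 3.8. The causality-based stopping criteria use the assessed relationship directly ('related' or 'at least possibly related'), not a SAP derivation.

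**Step 4: find what one omitted subject is worth.** Each dose group has 6 active subjects (protocol section 3.1). One subject dropped from a numerator changes that dose level's incidence by 1/6 = 0.167, or 16.7 percentage points. For the overall treatment-related row, this requires that the subject has no other TEAE that is possibly related or lacks a causality assessment. For a preferred-term row, the same condition applies within that term.

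**Step 5: apply the fix.** With 'Possibly Related' or 'Related' as the qualifying set and missing still counted, 2 of 2 causal categories are captured.

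**The case against.** The best reply is that the SAP phrase sets a threshold, possibly or stronger, and is not a list of strings to match. On that reading an event judged 'Related' qualifies plainly and nothing is lost. The documents support this as the intent. The protocol groups the two upper categories, its stopping rules speak of events at least possibly related, and the SAP counts even a missing assessment as related. A rule that counts missing causality but drops an explicit 'Related' would be absurd. The eCRF and the TFL shells are not available, so the coded values cannot be checked. The all-cause tables also report AE incidence and severity in full.

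Most of this stands, and it limits the point. A reader might infer that every event called 'Related' will certainly disappear from the treatment-related tables. The documents do not support that: no passage excludes 'Related', and the loss requires both literal matching and an eCRF that follows Appendix 1. Nor does the SAP confine the flag to its three named terms, since missing causality also qualifies.

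A reader might also expect injection-site reactions to be the events lost, because all CPT31-treated rats in the single-dose study had them (protocol section 1.4.1). That is not established either. Section 1.7 names such reactions as a risk of subcutaneous injection itself, so they could be graded 'Possibly Related', which the SAP captures on any reading.

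The reply does not remove the mismatch. It relies on the programmer inferring an intent that the governing document does not state. If the eCRF instead offers possibly, probably and definitely, data collection departs from Appendix 1. The documents need reconciling in either case.

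**Conclusion.** The point holds as a mismatch in a stated derivation rule. SAP 8.6.1 names two categories that the protocol does not define, omits the protocol's strongest one and gives no mapping. Applied literally to data on the Appendix 1 scale, it gives a wrong result: 'Related' is left out and missing is counted. The consequence is confined to the treatment-related TEAE summaries.

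The undercount cannot be estimated, because the documents do not show how many events will be graded 'Related' or how the flag will be programmed. It is zero if 'Related' is read as meeting the threshold. At worst, on literal matching, all 'Related' events are omitted from these summaries. The 16.7-point step is the effect of one omitted subject at one dose level under the conditions in the working, not a forecast.

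**What to change.** Before database lock, amend SAP 8.6.1 so that a treatment-related TEAE is one whose relationship is 'Possibly Related' or 'Related' as defined in protocol Appendix 1. Keep the existing rule that a missing relationship counts as related. Confirm that the eCRF offers the same four categories, then align the ADaM flag specification and the TFL shells. If the eCRF is found to use a different scale, reconcile it with Appendix 1 and write an explicit mapping into the SAP.

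The cost is one line of SAP text and matching edits to the programming specifications. If the eCRF follows Appendix 1, no protocol amendment and no change to collected data is needed.
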